Two core mechanisms – security and connection, and emotion regulation – are crucial to adolescent mental health in a context of social unrest. This project aims to support parents so that they can provide a safe and trustful environment to meet adolescents' needs after experiencing traumatic events (Gewirtz, Forgatch, & Wieling, 2008). Given the current social unrest, parents and adolescents need emotion regulation strategies that can promote positive affective change and facilitate empathy and reconciliation in families and communities (Cehajic-Clancy et al., 2016).

The content design of prevention and intervention programmes combines mindfulness skills with psychoeducation as a strategy for promoting security, connection, and emotion regulation (Chambers et al., 2009). Mindfulness training has been widely adopted as a therapeutic approach for reducing emotional distress and promoting psychological well-being, including PTS (Banks et al., 2015; Gu et al., 2015). A study in Israel showed that after being presented with anger-inducing information related to political conflict, participants in a mindfulness workshop were more supportive of conciliatory policies and the effect was mediated by a reduction in perceived threat and improvement in emotion regulation (Alkoby et al., 2017). In emotionally charged situations that may lead to verbal and physical aggression, mindfulness on the soles of the feet is a specific technique that enable individuals to manage their emotional arousal by shifting the focus of attention to a neutral physical body part (Singh et al. 2011). A recent study of Chinese adolescents suggested that teaching parents Mindfulness on the Soles of the feet could reduce the aggressive behaviour of their adolescent children (Ahemaitijiang et al., 2019). A pilot study of Hong Kong secondary school students is in progress.

Hypotheses of the study

The current study will test the following three hypotheses based on the literature:

- (i) Parents participate in a brief mindful parenting program will experience less depressive symptoms, anxiety symptoms, post-traumatic stress symptoms, family conflicts, and higher family functioning and interpersonal mindfulness than parents from wait-list control.
- (ii) Effects of the program will sustain at 3-month follow up.
- (iii) Parents with higher exposure to political unrest will predict the severity of the symptoms at pretest and follow-up.

RESEARCH PLAN AND METHODOLOGY

Study design

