This study uses a multi-site, randomized control trial. The effects of this intervention will be tested using a two-arm randomized controlled trial, comparing the mindful parenting program (Arm 1), to waitlist control group (Arm 2). Assessments will be made before (T0), 1-month follow up (T1), and 3-month follow-up (T2). The programme effects will be tested using both between-subject (comparison of the two arms) and within-subject (comparison of measures at T1, T2, and T3).

Sample size estimation. An estimated 340 parents will be recruited and randomised into an intervention group and a waitlist control group. The sample estimation is based on an expected effect size of .33 for family functioning in the PI's pilot study, with an estimated drop-out rate of 15%, a two-tailed α error of 5%, 80% power, and a test of two independent groups.

Recruitment of participants. Inclusion criteria are: (1) parents of an adolescent with the age between 10 to 21; (2) parents with a score of Patient Health Questionnaire (PHQ-9) score of 2 or above. Exclusion criteria are: 1) parents with current self-reported psychiatric diagnoses of psychosis, alcohol or substance abuse, 2) parents experiencing personal or family crisis in last six months; (3) parents cannot speak Chinese.

The research project will be announced and promoted in five non-governmental organizations, and social media. All interested parents will be given an information sheet and a four minute video explaining the nature of the study. After providing consent to participate the study, a research assistant who is blinded to the personal data of the participants, will administer the random assignment using computer generated programming. Participants will be randomly assigned to mindful parenting program (Arm 1), or waitlist control group (Arm 2).

Procedures

Program plan. The themes and content are based on a brief mindful parenting program developed by the same principal investigator (Lo et al., 2016, Lo et al., 2019). Psychoeducation of stress and coping in the context of parenting relationship is infused. Instructors for the program possess a PhD in psychology or social work, a specialist in psychiatry, and foundational professional training in mindfulness-based cognitive therapy.

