Implementation and assessment. After the first assessment (T0), caregivers who meet inclusion criteria will be randomized into Arm 1 or Arm 2. After the intervention, two time points will be used to assess the intervention outcome and sustainable effect at one month and three month. Programs are delivered in group format and will be conducted in five sites, including the P-I's university and the service units of NGO collaborators. To ensure intervention fidelity, all program sessions will be audio-recorded and an independent rater will listen to 20% of the selected clips on random basis, and assess whether each element in the intervention protocol has been implemented with consistency. Higher concordance rates will signify greater fidelity to the intervention protocol, which will be carefully monitored throughout the study.

An Ethical approval for this study has been obtained from the Research Office of the Hong Kong Polytechnic University.

Measures

All measures of the variables are summarized in Table 1 below. In line with the study objectives and hypotheses, primary outcome variables include parental depression. Secondary outcome measures include anxiety, post-traumatic stress, perceived family functioning, family conflicts, and interpersonal mindfulness.

Data Analyses

Quantitative data analyses: Intervention effects. All analyses will be carried out according to the intention-to-treat approach. (Moher et al., 2010). MANOVA will be used to evaluate the effects of the mindful

parenting (Arm 1), relative to waitlist control group (Arm 2), and the analyses of the primary and secondary outcome measures. In addition to the immediate programme effects, outcomes measured at T1 and T2 will be compared, to assess whether maintenance effects will be sustained at 3-months.

Table 1. Outcome variables and measures

Study variables and measures
Depression - Measured by the Patient Health Questionnaire (PHQ-9, Kroenke et al., 2001), 9 items
Anxiety - Measured by the Generalized Anxiety Disorder 7-item (GAD-7, Kroenke, et al., 2016), 7 items
Post-traumatic stress - measured by the International Traumatic Questionnaire (ITQ, Cloitre et al., 2009), 6 items
Family functioning - Measured by 5 item, Family APGAR Scale (Smilkstein, Ashworth, & Montano, 1982), with five subscales in adaptation, partnership, growth, affection, and resolve.
Family conflict - measured by Conflict Tactics Scale (CTS-2, Straus & Gelles, 1979), 16 items

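### The 3-month maintenance hypothesis is tied only to a T1-versus-T2 comparison; no between-arm contrast at T2 is specified

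*Combined protocol and SAP*

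**What the plan says.** Hypotheses of the study, item (ii), reads "Effects of the program will sustain at 3-month follow up". Under Data Analyses, the only sentence directed at that question says that "outcomes measured at T1 and T2 will be compared, to assess whether maintenance effects will be sustained at 3-months". It does not say whether this is done within Arm 1, pooled over arms, or as an arm-by-time comparison, and it gives no rule for deciding that an effect has lasted.

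Three other statements bear on the point, and none fixes a contrast at T2:

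- Study design: "The programme effects will be tested using both between-subject (comparison of the two arms) and within-subject" comparisons. The between-arm part has no time point.
- Data Analyses: a MANOVA assesses Arm 1 "relative to waitlist control group (Arm 2), and the analyses of the primary and secondary outcome measures". Again no time point is given.
- Implementation and assessment: "After the intervention, two time points will be used to assess the intervention outcome and sustainable effect at one month and three month". No comparison is named.

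The time labels also disagree. Study design sets the schedule as "Assessments will be made before (T0), 1-month follow up (T1), and 3-month follow-up (T2"), then describes the other comparison as "within-subject (comparison of measures at T1, T2, and T3"). No T3 is defined.

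The documents do not say when, relative to T2, the waitlist arm receives the programme.

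**The concern.** A lasting programme effect is a difference between arms that is still present at T2. A T1–T2 comparison estimates something else. Within Arm 1 it estimates that arm's own change, which mixes fading of the effect with any time trend and takes no account of what the waitlist arm does. As an arm-by-time comparison it estimates the change in the arm difference, which is zero both when the effect is fully kept and when there was never an effect.

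In either form, maintenance would show itself as no change. If a non-significant result were read that way, low power would count in favour of the hypothesis. At stake is whether a published claim of benefit at 3 months rests on a controlled estimate at 3 months. Leaving the contrast open also allows it to be chosen after the results are seen.

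**Working it through.** **Inputs from the protocol (Sample size estimation).** N = 340, drop-out 15%, effect size 0.33 (given for family functioning, read here as SD units), two-sided α = 0.05, power 80%, two independent groups.

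**Assumptions.** 1:1 allocation, SD = 1 at each time, T1–T2 correlation r = 0.6 (range 0.5 to 0.8), no clustering by programme group.

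**1. The plan's own figure.** n per arm = 2(1.960 + 0.842)²/0.33² = 144.2, rounded up to 145, so 290 in total. 290/0.85 = 341.2, or 342. The stated 340 reproduces. Expected completers per arm: 340 × 0.85/2 = 144.5.

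**2. What each comparison estimates.** Let D1 and D2 be the arm differences at T1 and T2.

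- Hypothesis (ii) requires D2 to be different from zero.
- Arm-by-time estimates D2 − D1, which is 0 if the effect is kept and 0 if it never existed.
- Within Arm 1 estimates that arm's mean at T2 minus its mean at T1. It is the same whether or not the waitlist arm improves.

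In simulation (144 per arm, 4,000 runs), the within-Arm-1 test used alone is non-significant in about 95% of trials in all three of these cases: effect kept, never an effect, waitlist caught up by T2. The between-arm test at T2 is significant in about 80%, 5% and 5% respectively.

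**3. Power of the T1–T2 comparison to detect loss of half the effect (0.165 SD), noncentral t.** Between-arm SE = √(2(1−r)) × √(2/144.5). Within-Arm-1 SE = √(2(1−r)/144.5).

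| r | Between-arm SE | Power | 95% half-width | Half-width / 0.33 | Within-Arm-1 SE | Power |
|---|---|---|---|---|---|---|
| 0.5 | 0.1176 | 29% | 0.232 | 70% | 0.0832 | 50% |
| 0.6 | 0.1052 | 35% | 0.207 | 63% | 0.0744 | 60% |
| 0.7 | 0.0911 | 44% | 0.179 | 54% | 0.0644 | 72% |
| 0.8 | 0.0744 | 60% | 0.146 | 44% | 0.0526 | 88% |

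So even an observed change of exactly zero in the arm difference is compatible with losing 44% to 70% of the planned effect.

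**4. The more favourable two-step rule.** Suppose an effect is called sustained when the unadjusted T1 arm contrast significantly favours Arm 1 and the T1–T2 comparison is non-significant. Simulated probability of that conclusion (144 per arm; r = 0.6 with 10,000 runs; range over r = 0.5 to 0.8 in brackets):

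| Truth | T1–T2 within Arm 1 | T1–T2 between arms |
|---|---|---|
| Never an effect | 2% | 2% |
| Effect fully kept | 76% | 76% |
| Half the effect lost by T2 | 30% (9–35%) | 49% (29–52%) |
| Waitlist fully catches up by T2 | 76% (76–78%) | 7% (0.3–12%) |
| Both arms worsen 0.25 SD, effect kept | 5% (0.1–9%) | 76% |

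A rough check on the second row: 0.798 (power at T1) × 0.95 = 0.758.

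**5. Power of a between-arm contrast at T2.** Unadjusted SE = √(2/144.5) = 0.1176. Power is 80% for 0.33 SD and 29% for 0.165 SD. Adjusted for T0 at an assumed T0–T2 correlation of 0.5, SE = 0.1176 × √(1 − 0.25) = 0.102, and power is 90% and 36%.

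**The case against.** The strongest reply is that the plan should be read as a whole. Hypothesis (ii) presupposes the effect in hypothesis (i), and the key sentence begins "In addition to the immediate programme effects, outcomes measured at T1 and T2 will be compared", so the natural sequence is to show an arm difference and then look at change. Both follow-ups are said to serve outcome and sustained effect, and an arm-by-time MANOVA over both would fit the text. On this view the gap is one of wording.

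Much of this stands. A T2 contrast is not excluded, the two-step sequence does deal with an effect that never existed, and catch-up and common worsening are mainly problems of the within-Arm-1 reading. Common worsening also makes a claim of maintenance less likely, so it costs sensitivity and does not create a false claim. The decision rule in the illustration is not in the documents; nothing there says that non-significance will be read as maintenance.

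It is also fair that a T2 contrast alone would not settle persistence. With half the effect lost it is significant in 29% of trials (36% adjusted), close to the 30% for the two-step rule within Arm 1. That is why a second estimate with an interval is needed.

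What does not stand is that the reading as a whole supplies the missing analysis. On every reading offered, no between-arm estimate at T2 is written down, and a partly lost effect can still be called sustained.

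**Conclusion.** The concern holds as a gap in the specified analysis of a stated hypothesis. The sample size is not in question. The only analysis explicitly directed at hypothesis (ii) cannot alone show a programme effect at 3 months, and no between-arm contrast at T2 is specified.

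That conclusion needs no numerical assumption. The sizes do: they rest on 1:1 allocation, 15% drop-out, 0.33 SD (planned for family functioning, whereas the primary outcome is PHQ-9 depression), r between 0.5 and 0.8, single-outcome t-tests in place of the MANOVA, and a reader who takes non-significance as maintenance. They also assume independent participants, which is optimistic for a programme delivered in groups. Under those assumptions the halved effect is a problem on both readings, and waitlist catch-up is serious only within Arm 1.

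**What to change.** Specify the following before analysis:

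1. Test hypothesis (ii) by the arm difference at T2 adjusted for the T0 value, with a 95% CI, one model per outcome and PHQ-9 first.
2. Report beside it the T1-to-T2 change in the arm difference, with its 95% CI, as the estimate of persistence. One repeated-measures linear model per outcome with arm, time (T1, T2), arm by time and T0 score gives both. Any group or site term adopted for the main analysis belongs here too.
3. State that maintenance will not be inferred from a non-significant T1–T2 difference.
4. State whether the waitlist arm is still untreated at T2. If it is not, limit the controlled conclusion to T1 and describe T2 as uncontrolled.
5. Reconcile the labels T1, T2, T3 with T0, T1, T2.

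The cost is one extra model per outcome beside the MANOVA, using assessments already planned. N need not change if the T2 effect is the planned 0.33 SD (80% power, before any adjustment). The limits remain: about 29–36% power for 0.165 SD, and a persistence estimate good only to about ±0.15 to 0.23 SD, so the intervals must be read and not the p-values alone. If the waitlist arm is treated before T2, no reanalysis restores a controlled test of hypothesis (ii).
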